7.4.1 Investigators Global Assessment (IGA)

The IGA should be performed at Screening and each study visit (Baseline, Weeks 1, 3, 6, 9, 12, 16, 26, 39 and 52) prior to performing the lesion count. The IGA is intended for the global evaluation of papulopustular rosacea. Background nontransient erythema and telangiectasias should not be assessed as part of the IGA. The IGA score represents the subject's condition at the time of the evaluation.

The following categories will be used from the IGA scale to perform the global evaluation of papulopustular rosacea:

CONFIDENTIAL

Version Date: 31 March 2017

Investigators Global Assessment (IGA) Scale

Grade	Grading Scale Score	Description of Papulopustular Rosacea Disease Status
Clear	0	No inflammatory papules or pustules.
Almost clear	1	Very few with 1 or 2 inflammatory papules/pustules.
Mild	2	Several (3-10) small inflammatory papules/pustules.
Moderate	3	11 to 19 small or large inflammatory papules/pustules and no nodules.
Severe	4	Numerous (≥ 20) small and or large inflammatory papules/pustules, and up to 2 nodules, (at baseline).

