## 5.0 Statistical Methodology

All statistical analyses will be performed using SAS® software version 9.3. Unless otherwise specified, all statistical tests will be two-sided with a significance level of 0.05. Continuous parameters will be summarized by N (number of non-missing observations), mean, standard deviation, median, minimum, and maximum. Categorical parameters will be summarized by count and percent.

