### 5.1 Sample Size Determination

The primary objective of the study is to show superiority of Omiganan over vehicle for the treatment of rosacea in patients with severe papulopustular rosacea (IGA Grade 4 with baseline inflammatory lesion count  $\geq 30$ ). A sample size calculation was made for two co-primary endpoints. For change from baseline in inflammatory lesions, it is assumed that in the Omiganan treatment arm, subjects will have an average reduction of 13.5 inflammatory lesions, compared to 4 in the vehicle arm. The standard deviation is assumed to be 12. For 95% power, a sample size of 86 subjects (43 per group) is needed. For IGA, it is assumed that Clear or Almost clear (IGA of 0 or 1) at Week 12 has lesser power than 2 point reduction. It is also assumed that 17% of the subjects in the Omiganan treatment arm versus 6% in the vehicle arm will have IGA of clear or almost clear at Week 12. For 95% power and using a Fisher's Exact test, 450 subjects (225 in each arm) are needed. Therefore, the number of subjects needed to ensure at least 95% power for both endpoints is 450.

The sample sizes were calculated using 95% power in order to ensure 90% power across two Phase 3 studies.

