## 6.2 Missing Data

The primary method of dealing with missing data is multiple imputation (MI) technique. All co-primary and secondary endpoints will be analyzed using MI for missing data. As a sensitivity analysis, Observed Case and Baseline Observation Carried Forward (BOCF) will be utilized for the co-primary endpoints only.

The MI technique will be implemented as follows:

a) 100 imputed datasets will be generated to impute missing data using the below SAS code.

1) For inflammatory lesions

```
Proc MI NIMPUTE=100 SEED=20170531  
MIN = . 0 0 0 0 0 0  
MAX = . . . . . . .  
ROUND = . 1 1 1 1 1 1;  
class sex;  
var sex base w1 w3 w6 w9 w12;  
fcs reg(w1) reg(w3) reg(w6) reg(w9) reg(w12);  
run;
```

2) For IGA

```
Proc MI NIMPUTE=100 SEED=20170531  
MIN = . 0 0 0 0 0  
MAX = . 4 4 4 4 4  
ROUND = . 1 1 1 1 1;  
class sex;  
var sex w1 w3 w6 w9 w12;  
fcs reg(w1) reg(w3) reg(w6) reg(w9) reg(w12);  
run;
```

b) The 100 imputed datasets will each be analyzed separately by the methods described in Section 5.4.2.

1) For inflammatory lesions, individual LS means and associated standard errors as well as estimates and standard errors from the pairwise comparison of treatments from the analysis of each imputation will be combined into single estimates, standard errors, and p-value using PROC MIANALYZE as displayed below.

```
Proc MIANALYZE;  
Modeleffects estimate;  
Stderr stderr;  
run;
```

The p-value for the treatment by center interaction will be based on the average of p-values from each the analyses of each imputation.

- 2) For IGA, estimates of the event rates will be based on the average of rates from each imputation. The CMH test statistic from the analysis of each imputation will be converted to a Normal Z score by taking the square root and adjusting for direction (change to a negative value if Omiganan group is worse than Vehicle). These Z scores (with SE=1) will be combined into a single p-value using PROC MIANALYZE as displayed below:

```
Proc MIANALYZE;  
Model effects estimate;  
Stderr SE;  
run;
```

Similarly, the p-values for the one-sided Fisher's Exact test of each imputation will be converted to a Normal Z score using the inverse normal function. These Z scores (with SE=1) will be combined into a single p-value using the same PROC MIANALYZE code.

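### SAP 6.2 imputes the five-grade IGA as a bounded, rounded normal variable without lesion counts, which biases the primary IGA rates; the power cost is small in most scenarios

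*SAP*

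**What the plan says.** SAP 6.2 makes multiple imputation the primary missing-data method for all co-primary and secondary endpoints, with 100 imputed datasets. For IGA:

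- The imputation variables are "var sex w1 w3 w6 w9 w12". Lesion counts, treatment arm and center are absent. Baseline IGA is also absent, but it is 4 for every eligible subject, so nothing is lost there.
- The method is "fcs reg(w1) reg(w3) reg(w6) reg(w9) reg(w12"), a normal linear regression at each visit, with minimum 0, maximum 4 and rounding to 1.
- Lesion counts are imputed in a separate call.
- The reported event rates are averages over the imputed datasets. The CMH statistics are turned into Z scores and pooled.

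Protocol 7.4.1 ties each IGA grade to a number of lesions: none; 1 or 2 ("Very few with 1 or 2 inflammatory papules/pustules"); 3–10; 11–19; 20 or more. Protocol 7.2.1 requires grade 4 and at least 30 lesions at Baseline.

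Observed Case and BOCF are planned as sensitivity analyses for the co-primary endpoints. Neither document states an expected dropout rate, a baseline lesion distribution or the expected spread of Week 12 grades.

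**The concern.** A linear model with normal errors suits a roughly symmetric variable away from its limits. IGA here is a five-level ordered score that starts at its maximum for everyone, and it may stay there for many subjects while a small group clears. If normal draws above 4 are discarded, the draws left are mostly below 4, so grade 4 is imputed too seldom and grades 2 and 3 too often. A 2-grade reduction needs only grade 2 or lower, so its rate rises. The rise is relatively largest where the true rate is lowest, in vehicle. The same smooth curve cannot reproduce a small cluster at grades 0 and 1.

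The model also ignores the lesion counts collected at every double-blind visit. Counts of 20 and 80 are both grade 4 and look identical to it, although the first subject is far closer to a lower grade.

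At stake are the primary ITT estimates of both IGA response rates, and to a lesser degree the power of the endpoint that sets the sample size. The missing treatment term is a separate defect, so the figures for this point come from comparisons with treatment arm in both models.

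**Working it through.** **Inputs from the documents.** "all statistical tests will be two-sided with a significance level of 0.05" (SAP 5.0). IGA 0/1 in "17% of the subjects in the Omiganan treatment arm versus 6% in the vehicle arm", and "For 95% power and using a Fisher's Exact test, 450 subjects (225 in each arm) are needed" (SAP 5.1). For lesions, "subjects will have an average reduction of 13.5 inflammatory lesions, compared to 4 in the vehicle arm"; "The standard deviation is assumed to be 12".

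**Assumed.** Missing Week 12 data of 10% and 20%; the grade distributions below.

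**1. The plan's own figures reproduce.** Summing Bin(x₁; 225, 0.17) × Bin(x₂; 225, 0.06) over all outcomes with two-sided Fisher p ≤ 0.05 gives power of 95.1%. For lesions, the noncentrality is (9.5/12) × √(43/2) = 3.67 on 84 df, which gives 95.2%.

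**2. Is there a pile-up at grade 4?** With baseline count B and a normal change, the share still at 20 or more lesions is Φ((B − 20 − mean reduction)/12).

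- B = 30, the entry minimum: omiganan Φ(−0.29) = 39%, vehicle Φ(0.50) = 69%, average 54%.
- B = 40, assumed: Φ(0.54) = 71%, Φ(1.33) = 91%, average 81%.

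So a pile-up is likely on the plan's figures, but its height depends on a baseline distribution that the documents do not give.

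**3. Hand illustration.** Take a vehicle-like spread of 6% at grade 0/1 (counted as 1), 4% at grade 2, 15% at grade 3 and 75% at grade 4. The mean is 0.06 + 0.08 + 0.45 + 3.00 = 3.59. The variance is 13.57 − 3.59² = 0.68, so the SD is 0.826. Draw from this normal distribution, cut at 4 and round:

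- Grade 4: (Φ(0.50) − Φ(−0.11))/Φ(0.50) = (0.690 − 0.457)/0.690 = 34%. If the bound is applied after rounding (cut at 4.5), it is (0.865 − 0.457)/0.865 = 47%. The true share is 75%.
- Grade 2 or lower: 0.093/0.690 = 14%, or 0.093/0.865 = 11%. True 10%.
- Grade 0/1: 0.0057/0.690 = 0.8%, or 0.0057/0.865 = 0.7%. True 6%.

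This ignores the earlier visits, which soften the effect, but it shows the direction.

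**4. Simulation of whole trials.** 225 per arm, IGA 0/1 at 17% vs 6%, dropout depending on the last IGA, 400 trials, 30 imputations, Z scores pooled as in SAP 6.2, unstratified Mantel-Haenszel test. The between-visit correlation is 0.8 and the IGA–lesion correlation 0.85. Vehicle grade 2 or lower is 18% (base) or 10% (skewed, most subjects at grade 4).

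| Scenario | Missing | IGA model | Vehicle 2-grade rate | IGA 0/1 difference | IGA Hochberg power |
|---|---|---|---|---|---|
| Base | none | – | 17.9% | 10.76 | 99.8% |
| Base | 10% | normal + arm | 19.4% | 10.69 | 99.2% |
| Base | 10% | ordinal + arm + counts | 18.1% | 10.84 | 99.0% |
| Base | 20% | SAP as written | 22.2% | 9.52 | 97.2% |
| Base | 20% | normal + arm | 20.9% | 10.61 | 98.5% |
| Base | 20% | ordinal + arm + counts | 18.1% | 10.91 | 99.0% |
| Skewed | none | – | 10.0% | 10.76 | 98.0% |
| Skewed | 10% | SAP as written | 12.0% | 10.07 | 95.8% |
| Skewed | 10% | normal + arm | 11.5% | 10.44 | 97.0% |
| Skewed | 10% | ordinal + arm + counts | 10.0% | 10.86 | 97.5% |
| Skewed | 20% | SAP as written | 14.2% | 9.27 | 88.2% |
| Skewed | 20% | normal + arm | 13.2% | 10.00 | 93.5% |
| Skewed | 20% | ordinal + arm + counts | 10.1% | 10.87 | 97.5% |

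The rows with arm in both models isolate the normal model without counts:

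- Vehicle 2-grade rate: +1.4 to +1.5 points at 10% missing, +2.8 to +3.0 at 20%.
- IGA 0/1 difference: lower by 0.15–0.42 at 10%, by 0.30–0.87 at 20%.
- Hochberg power: no loss (base) or 0.5 points (skewed) at 10%; 0.5 (base) or 4.0 (skewed) at 20%.

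With a between-visit correlation of 0.6 in the base scenario at 20% missing, the same comparison gives +3.2 points, −0.45 points and 1.8 points of power.

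Against complete data, normal + arm at 20% missing raises the 2-grade rate from 10.0% to 13.2% in vehicle and from 24.5% to 27.3% in omiganan (skewed scenario). The rise is similar in points but relatively much larger in vehicle.

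**5. Imputed subjects only, arm in the model.** In a responder-mixture simulation, grade 4 was imputed in 45–60% of dropouts (true 77%) and a vehicle 2-grade reduction in 12–18% (true 7%). Under two other grade distributions the figures were 19–25% (true 53–75%) and 24–31% (true 9–19%). Predictive mean matching with arm and counts recovered the true rates.

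**The case against.** **The power effect is near simulation noise.** Monte Carlo error is about 1–2 points. A separate set of 1,800 simulated trials per setting over three grade distributions, with arm in both models, compared bounded normal imputation with predictive mean matching plus counts. Hochberg power was 98.1/98.3, 96.1/96.8 and 93.9/94.1% at 10% missing, and 96.9/97.4, 95.4/96.1 and 90.9/92.3% at 20%: gains of 0.2–1.4 points. This stands. A reader might infer that the imputation model by itself undoes the planned 95% power. The documents do not support that as a general result, because only the skewed scenario at 20% missing shows a loss near 4 points.

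**The missing treatment term matters more for IGA 0/1.** In the base scenario at 20% missing, adding arm alone to the SAP model moves the difference from 9.52 to 10.61 points. Adding counts alone moves it only to 9.58. This also stands.

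**The grade distribution is assumed.** A reader might take it as planned that most subjects stay at grade 4. The documents give no such rate; SAP 7.0 says only that baseline counts vary widely.

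**Lesion counts may help less than simulated.** IGA is a global rating made before the count, and its descriptors also mention lesion size and nodules. That is fair, and it limits the benefit of adding counts. It does not rescue the normal model.

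**Separate runs can give one subject an incompatible count and grade.** A reader might count this as a further fault, but no planned test combines the two.

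**There are safeguards.** Early leavers have the Week 12 procedures (Protocol 7.2.3), and a final visit from Day 75 counts as Week 12 (SAP 6.1), which limits missing data. Observed Case and BOCF do not use this model. They show sensitivity but leave the primary estimate biased. No false-positive risk has been shown; the effect on the treatment difference is toward the null.

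**Conclusion.** The point holds as one of bias in the primary IGA estimates, with a scenario-dependent effect on power. Apart from the omitted treatment term, the bounded and rounded normal model:

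- raises the whole-trial vehicle 2-grade-reduction rate by about 1–2 points at 10% missing and 2–4 points at 20%;
- lowers the IGA 0/1 difference by about 0.3–1 point at 20% missing, and by less at 10%;
- costs under about 1.5 points of IGA power at 10% missing and about 0.5–4 points at 20%, most when grades pile up at 4.

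These sizes rest on assumed dropout of 10–20%, assumed grade distributions and correlations, and sequential imputation standing in for the SAP's FCS call. The ranges for imputed grades also reflect uncertainty over whether the bound acts before or after rounding. The direction of the 2-grade bias was the same in every scenario. The change is worth making because the biased rates are the ones that will be reported as primary.

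**What to change.** Make this change together with adding treatment arm, before unblinding. Replace the IGA block in SAP 6.2(a)(2) with one FCS model holding sex, treatment arm, baseline lesion count, lesion counts at Weeks 1–12 and IGA at Weeks 1–12. Then either:

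- impute IGA by predictive mean matching (FCS REGPMM) and drop MIN, MAX and ROUND for IGA, so that only observed grades can occur; or
- declare IGA as a class variable and use ordinal FCS LOGISTIC with the lesion counts as covariates.

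Derive IGA 0/1 and 2-grade reduction from the imputed grades. Keep Observed Case and BOCF as they are.

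The cost is SAP wording and a few lines of code, with no new data. With the ordinal model, rare grades may need merging at early visits, so the merging rule should be written down in advance.

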7.2.3 Withdrawal from Study Criteria

Reasons for discontinuation from the study include, but are not limited to, the following:

- Adverse Event
- Pregnancy
- Withdrawal By Subject
- Lost To Follow-Up. The Investigator will try to reach the subject, twice by telephone (document telephone calls) and once by certified letter, before considering the subject lost-to-follow-up. The lost to follow-up discontinuation will be reported on the appropriate eCRF, and a copy of the follow-up letter will be maintained in the Investigator's file.
- Study Terminated By Sponsor
- Physician Decision
- Non-Compliance with Study
- Other

All premature discontinuations from the study must be documented by the Investigator on the eCRF, and if due to an adverse event, on the Adverse Event Case Report page of the eCRF. All subjects should attempt to complete all visits and evaluations.

Subjects not completing the entire study should be fully evaluated (i.e., final double-blind Week 12 visit procedures performed during the double-blind period or the final open label Week 52 visit procedures during the open-label period). All subjects are free to withdraw from participating in this study at any time and for whatever reason, specified or unspecified, and without prejudice to his or her medical care by a physician. Subjects who withdrawal from the study will not be replaced.

CONFIDENTIAL

Version Date: 31 March 2017

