7.7.10 Efficacy Analysis

The co-primary endpoint of absolute change from baseline in inflammatory lesions will be analyzed using an Analysis of Covariance (ANCOVA) model, with treatment as a main effect, and center as a covariate. To investigate consistency of efficacy results across study centers, treatment by study center interaction will be tested at 0.10 level of significance, and if significant, it will be further explored.

The co-primary endpoint of IGA will be tested in the following manner: The 2 grade reduction, and the Clear or Almost Clear (0, 1) will be tested using the Hochberg procedure as follows: Statistical significance will be concluded if both endpoints are significant at a two-sided 0.05 level, or either endpoint is significant at a two-sided 0.025 level. Both IGA endpoints will be analyzed using a Cochran–Mantel–Haenszel (CMH) test, with center as the stratification factor. If the overall IGA

CONFIDENTIAL

Version Date: 31 March 2017

response rates are less than 10%, a Fisher's Exact test will be used to corroborate the CMH test. All tests of the co-primary endpoints will be analyzed.

If the co-primary endpoints of absolute lesion reduction and the two IGA endpoints (2 grade reduction, and Clear or Almost Clear (0, 1)) are both significant, the secondary endpoints will be analyzed sequentially in the order listed:

- Test first secondary endpoint at 0.05. If not significant, stop; otherwise,
- Test second secondary endpoint at 0.05. If not significant, stop; otherwise,
- Test third secondary endpoint at 0.05 using Hochberg (similar to the primary method). If not both IGA (0,1) and IGA 2 point reduction are significant, stop; otherwise,
- Test fourth secondary endpoint at 0.05 using the Hochberg method

For all efficacy analyses, small centers may be pooled in order to ensure sufficient cell counts for statistical testing.

Subgroup analyses (e.g. Gender, Age, Race, and Center) of the co-primary endpoints will be performed.

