#### **5.4.3 Efficacy Analysis**

The co-primary endpoint of absolute change from baseline in inflammatory lesions will be analyzed using an Analysis of Covariance (ANCOVA) model, with treatment as a main effect, and baseline inflammatory lesions and pooled center as covariates. To investigate consistency of efficacy results across study centers, treatment by center interaction will be tested at 0.1 level of significance, and if significant, it will be further be explored.

The co-primary endpoint of IGA will be tested in the following manner: the 2 point reduction and the Clear or Almost Clear (0, 1) will be tested using the Hochberg procedure as follows: Statistical significance will be concluded if both endpoints are significant at a two-sided 0.05 level, or if either endpoint is significant at a two-sided 0.025. Both IGA endpoints will be analyzed using a Cochran–Mantel–Haenszel (CMH) test with center as the stratification factor. If the overall IGA response rates are less than 10%, a Fisher’s Exact test will be used to corroborate the CMH test. All tests of the co-primary endpoints will be analyzed.

If the co-primary endpoints of absolute lesion reduction and the two IGA endpoints (2 point reduction, and Clear or Almost Clear (0, 1)) are significant, the secondary endpoints will be tested sequentially in the order listed as follows:

- Test first secondary endpoint at 0.05. If not significant, stop; otherwise,
- Test second secondary endpoint at 0.05. If not significant, stop; otherwise,
- Test third secondary endpoint at 0.05 using Hochberg (similar to the primary method). If not both IGA (0,1) and IGA 2 point reduction are significant, stop; otherwise,
- Test fourth secondary endpoint at 0.05 using the Hochberg method.

For all efficacy analyses, small centers may be pooled in order to ensure sufficient cell counts for statistical testing.

Subgroup summaries (e.g. Gender, Age, Race, and Center) of the co-primary endpoints will be performed.

[figure not shown]

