#### 6.1 Baseline and Follow-Up Visits

Visits and time points (Double-blind period: baseline, interim [Weeks 1, 3, 6 and 9], final visit [Week 12]; Safety extension period: Weeks 16, 26, 39 and Week 52) for all analyses will be as record on the eCRFs , except as noted below. Baseline will be the later of the non-missing values from the Screening and Baseline/Day 1 visits scheduled to occur prior to receiving study medication. Unscheduled visits will not be used in any analyses but will be included on data listings.

If a subject does not complete the Double-Blind Study Period, the final double-blind visit (Week 12) will be reassigned to a scheduled visit based on the relative day ranges in the following table (where Day 1 is the first day of dosing). If a result already exists for the calculated visit or the calculated visit was not a scheduled visit, the next scheduled visit will be assigned.

Study Day Range	Calculated Visit
$2 \leq \text{Study Day} \leq 15$	Week 1
$16 \leq \text{Study Day} \leq 32$	Week 3
$33 \leq \text{Study Day} \leq 53$	Week 6
$54 \leq \text{Study Day} \leq 74$	Week 9
$\text{Study Day} \geq 75$	Week 12

If an Open-Label subject does not complete the study, the final open-label visit (Week 52) will be reassigned to a scheduled visit based on the relative day ranges in the following table. If a result already exists for the calculated visit or the calculated visit was not a scheduled visit, the next scheduled visit will be assigned.

Study Day Range	Calculated Visit
$89 \leq \text{Study Day} \leq 148$	Week 16
$149 \leq \text{Study Day} \leq 228$	Week 26
$229 \leq \text{Study Day} \leq 319$	Week 39
$\text{Study Day} \geq 320$	Week 52

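### The treatment-by-center check averages 100 imputation p-values, so it is not the stated 0.10-level test once Week 12 lesion counts are imputed (minor)

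*SAP*

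**What the plan says.** Protocol 7.7.10 states that "treatment by study center interaction will be tested at 0.10 level of significance, and if significant, it will be further explored". SAP 5.4.3 repeats the level: "treatment by center interaction will be tested at 0.1 level of significance". The test belongs to the lesion-count ANCOVA, which in the SAP has treatment, baseline count and pooled center.

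SAP 6.2 generates 100 imputed datasets. Lesion counts are imputed from "var sex base w1 w3 w6 w9 w12", so neither treatment nor center is in the imputation model. The treatment contrast and the IGA statistics are combined with PROC MIANALYZE. The interaction is handled differently: "The p-value for the treatment by center interaction will be based on the average of p-values from each the analyses of each imputation". Neither document adjusts the 0.10 threshold for this.

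SAP 6.2 also plans sensitivity analyses: "Observed Case and Baseline Observation Carried Forward (BOCF) will be utilized for the co-primary endpoints only". It does not say whether the observed-case analysis includes the interaction test.

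SAP 6.1 covers subjects who leave early: "the final double-blind visit (Week 12) will be reassigned to a scheduled visit based on the relative day ranges in the following table". A termination visit before Day 75 normally moves to an earlier week, unless that week already has a result. When it moves, Week 12 is left to be imputed.

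**The concern.** A test has level 0.10 if its p-value falls below 0.10 in 10% of trials when there is no interaction. Each imputed dataset gives a p-value that is roughly uniform in that case. The average of 100 such values, which are correlated but not identical, is not uniform. Comparing it with 0.10 is therefore not a 0.10-level test, and the actual level depends on how much is missing and how it is imputed.

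What is at stake is the trigger for further exploration of center differences in a trial of about 50 sites in nine countries. If the trigger fires less often than its stated level implies, real heterogeneity is flagged less often, and a report that the interaction was not significant at 0.10 would describe a stricter test than the one named.

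**Working it through.** **Inputs from the documents.** 450 subjects, 1:1; mean reductions 13.5 and 4, SD 12 (SAP 5.1); pools of at least 16 (SAP 6.3), so at most 450/16 = 28 pools and 27 interaction degrees of freedom; 100 imputations from sex, baseline and visits, minimum 0, rounded (SAP 6.2); level 0.10 (SAP 5.4.3).

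**Assumed, because the documents do not give them.** Week 12 missing rate 3% to 20%; visit correlation 0.3 to 0.85; dropout spread over the visits or at Week 12 only; 10 or 28 pools; dropout completely at random.

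**Step 1: the stated level with complete data.** The ANCOVA interaction F test rejected in 0.101 of about 32,600 simulated trials without interaction. This reproduces 0.10.

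**Step 2: the averaged p is not uniform.** A uniform p-value has variance 1/12, or SD 0.289. Under the null, the mean within-trial SD of the 100 p-values was 0.107 at 10% missing and 0.149 at 20%. By the law of total variance, the SD of the average is at most √(1/12 − 0.107²) = 0.268 and √(1/12 − 0.149²) = 0.247. This shows non-uniformity. It does not settle the direction of the error at 0.10.

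**Step 3: null rejection at 0.10 under the SAP's imputation model** (10% / 20% missing). The standard error is √(p(1−p)/trials), for example √(0.070 × 0.930/4000) = 0.004.

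| Setting | Averaged p | Individual imputed datasets | Observed-case F |
|---|---|---|---|
| 28 pools, correlation 0.6, dropout over visits (three runs, 3,000–4,000 trials) | 0.059–0.070 / 0.040–0.047 | 0.094–0.101 / 0.095–0.107 | 0.096–0.107 / 0.095–0.112 |
| Same, Week 12 only missing (2,000) | 0.063 / 0.037 | 0.096 / 0.095 | 0.094 / 0.102 |
| Correlation 0.3 (1,500) | 0.073 / 0.037 | 0.114 / 0.111 | 0.121 / 0.103 |
| Correlation 0.8 (1,500) | 0.071 / 0.047 | 0.109 / 0.112 | 0.123 / 0.106 |
| 10 pools (1,500) | 0.053 / 0.045 | 0.088 / 0.102 | 0.091 / 0.093 |
| Autoregressive 0.85, Week 12 only (1,500) | 0.088 / 0.072 | 0.102 / 0.097 | 0.106 / 0.097 |

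Runs with correlation 0.8 and later dropout (40 imputations, 2,000 trials) gave 0.081–0.085 / 0.064–0.071. Two implementations with correlation 0.8 and only Week 12 missing gave 0.064 / 0.044 and 0.092 / 0.073. At 10% they differ by 0.028 with a standard error of about 0.009, so other modelling details matter too. That is why a range is reported.

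At 3% missing the averaged p gave 0.089. At 5% it gave 0.078, 0.084 and, with correlation 0.8 and later dropout, 0.086–0.097.

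The individual imputed datasets stay near 0.10, so under this imputation model the averaging produces the level loss.

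**Step 4: other combinations under the null** (10% / 20% missing).

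- SAP imputation, multi-parameter pooling: Wald 0.025 / 0.007; D2 0.015 / 0.002.
- Treatment added to the imputation, averaged p: 0.069–0.074 / 0.037–0.048.
- Treatment and center main effects added, averaged p: 0.069 / 0.046.
- Treatment, center and their interaction added: averaged p 0.196–0.229 / 0.362–0.499; pooled Wald 0.096 / 0.093; D2 0.098 / 0.101.

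**Step 5: detection at 20% missing** (between-center SDs of 6 and 3 lesions are assumptions).

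- SD 6, interaction only at Week 12: observed-case 0.77, single imputed dataset 0.64, averaged 0.60. The imputation model accounts for 0.13 and averaging for 0.04.
- SD 3, interaction equal at all visits: 0.28, 0.27, 0.20. Here averaging accounts for 0.07 and the imputation model for 0.01.
- SD 6, equal at all visits: observed-case 0.77, averaged 0.77, no loss.

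**The case against.** **The consequence is close to nil.** This stands. The check gates nothing. Center results appear whatever its p-value: "Subgroup summaries (e.g. Gender, Age, Race, and Center) of the co-primary endpoints will be performed", and SAP 6.3 adds center and pooled-center summaries. A reader might infer that the co-primary conclusions or their type I error are affected, or that center heterogeneity would go unseen. The documents support neither.

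**The missing rate may be low.** This stands in part. Protocol 7.2.3 says "Subjects not completing the entire study should be fully evaluated", SAP 6.1 counts visits from Day 75 as Week 12, and a visit whose assigned week is already filled moves to the next one. These limit missing Week 12 values but do not remove them.

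**Smaller spread does not prove too few rejections.** This is right. Take U uniform, and V = 0.19 − U when U < 0.19, otherwise V = U. Both are uniform with correlation 0.986, yet their average is below 0.10 with probability 0.19. It is tempting to infer that averaged p-values are always conservative. Step 4 shows the reverse for a fully interacted imputation model.

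**Single figures would overstate what is known.** This also stands. The level depends on inputs that the documents do not give. Nor can all of the detection loss against observed cases be charged to averaging (step 5).

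**An observed-case interaction test may already be intended.** That reading is natural, since SAP 5.4.3 places the interaction test with the lesion ANCOVA, but SAP 6.2 does not state it. The averaging sentence is the only explicit rule for this p-value.

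**Conclusion.** The point holds and is minor. As written, the check does not have the 0.10 level that both documents state once Week 12 counts are imputed. Under the SAP's imputation model the actual level is roughly 0.05 to 0.09 at 10% missing and 0.04 to 0.07 at 20%. At 3% to 5% the shift is small, with a level of about 0.08 to 0.10.

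That the averaged p is not uniform is a matter of principle. That it rejects too rarely is a simulation result for this imputation model, with completely random dropout and the assumed ranges of visit correlation, dropout pattern and pool number. How much detection is lost depends further on the size and timing of any interaction, and for a large constant interaction it is essentially none.

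**What to change.** In SAP 6.2, replace the averaging sentence with: *The treatment-by-pooled-center interaction will be tested at the 0.10 level with the F test from the observed-case ANCOVA (treatment, baseline lesions, pooled center, treatment by pooled center).* In the simulations this test stayed near 0.10 at every missing rate tried.

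The change is one sentence, to be made before unblinding. The PROC MI code for the co-primary analysis is untouched. The downside is that the check uses fewer subjects than the imputed ITT set and relies on dropout not distorting center effects.

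If an imputed version is also reported, run a separate imputation that includes treatment, center and their interaction, and pool with a multi-parameter Wald or D2 test. Changing only the pooling rule makes the check more conservative. Adding only treatment, or only the treatment and center main effects, does not restore the level. Whether treatment belongs in the co-primary imputation model is a separate question that this point does not address.
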